8.4. Emergency Unblinding of Treatment Assignment

Not applicable.

8.5. Pregnancy

Pregnancy, in and of itself, is not regarded as an AE unless there is suspicion that study drug may have interfered with the effectiveness of a contraceptive medication or method. When a pregnancy has been confirmed in a subject during maternal or paternal exposure to study drug, the following procedures should be following in order to ensure subject safety:

- The investigator must notify the sponsor or its designee immediately.
- The study drug must be discontinued immediately (female subjects only; see Section 5.2.5 for the maximum permitted duration of study drug interruption).
- The investigator must complete and submit the Incyte Clinical Trial Pregnancy form to the sponsor or its designee within **24 hours** of learning of the pregnancy.

Data on fetal outcome and breastfeeding are collected for regulatory reporting and drug safety evaluation. Follow-up should be conducted for each pregnancy to determine outcome, including spontaneous or voluntary termination, details of the birth, and the presence or absence of any birth defects, congenital abnormalities, or maternal and/or newborn complications, by following until the first well-baby visit. Pregnancy should be recorded on a Clinical Trial Pregnancy form and reported by the investigator to the sponsor or its designee. Pregnancy follow-up information should be recorded on the same form and should include an assessment of the possible causal relationship to the sponsor's study drug to any pregnancy outcome, as well as follow-up to the first well-baby visit or the duration specified in local regulations, whichever is later. Refer to the Incyte Reference Guide for Completing the Clinical Trial Pregnancy Form.

Any SAE occurring during pregnancy must be recorded on the SAE report form and submitted to the sponsor or designee.

8.6. Warnings and Precautions

Special warnings or precautions for the study drug, derived from safety information collected by the sponsor or its designee, are presented in the [INCB053914 IB](#). Additional safety information collected between IB updates will be communicated in the form of Investigator Notifications (INs). Any important new safety information should be discussed with the subject during the study, as necessary. If new significant risks are identified, they will be added to the ICF.

8.7. Data Monitoring Committee

A formal Data Monitoring Committee will not be used for this study. The sponsor will continuously monitor safety through frequent contact with the treating investigators, review of the clinical data, and formal study meetings. Routine (weekly or biweekly) teleconferences will be held during the dose escalation and expansion phases among participating study sites to provide subject-by-subject updates on current study status, interim toxicities reported, and any other pertinent information. Adverse event and laboratory data entered into the clinical database will be reviewed periodically for trends and evolving safety signals. Lastly, formal review

CONFIDENTIAL

CONFIDENTIAL

meetings will be conducted with investigators during the study to establish consensus on the safety and tolerability of a given dose, based on the collective experience of the group.

8.8. Product Complaints

The sponsor collects product complaints on study drugs and drug delivery systems used in clinical studies in order to ensure the safety of study participants, monitor quality, and facilitate process and product improvements.

All product complaints associated with material packaged, labeled, and released by the sponsor or its designee will be reported to the sponsor. All product complaints associated with other study material will be reported directly to the respective manufacturer.

The investigator or his/her designee is responsible for reporting a complete description of the product complaint and any associated AEs via email or other written communication to the sponsor contact or respective manufacturer as noted in the packaging information. Any AE associated with a product complaint should be reported as described in Section 8.1.2 of this Protocol.

If the investigator is asked to return the product for investigation, he/she will return a copy of the product complaint communication with the product.

9. STATISTICS

9.1. Study Populations

The populations to be analyzed include the following:

The safety population is defined as all subjects who are enrolled and received at least 1 dose of study drug. All safety analyses will be based on the safety population.

The full analysis set (FAS) includes all subjects enrolled in the study who received at least 1 dose of study medication and have at least 1 postbaseline assessment or who discontinued treatment. All efficacy analyses will be based on FAS.

The PK/PD-evaluable population includes the safety population who has at least 1 valid PK/PD measurement.

9.2. Selection of Sample Size

9.2.1. Sample Size in Part 1

A 3 + 3 dose escalation design will be used in 2 disease-specific treatment groups. Dose escalation for TGA and TGB will proceed independently. Based on 3 + 3 algorithm, a minimum of 3 and up to 6 subjects will be enrolled at each dose level. The total sample size in Part 1 will depend on the frequency of DLTs and the number of dose levels tested before the MTD or PAD is reached. The details of the 2 dose-escalation groups are in Section 4.1.1.

CONFIDENTIAL

CONFIDENTIAL

9.2.2. Sample Size in Part 2

Part 2 will include up to 5 expansion cohorts to further evaluate the safety, tolerability, efficacy, PK and PD of RP2Ds selected from Part 1. Within each cohort, at least 5 and up to approximately 15 subjects will be enrolled and treated at the RP2D identified in the corresponding treatment group. With 5 subjects enrolled, there is an 83% probability of observing at least 1 responder if the true underlying response rate is 30%. The details of 5 expansion cohorts are in Section 4.1.2.

9.2.3. Sample Size in Part 3

Part 3 will use a 3 + 3 design to evaluate different doses of INCB053914 in combination with cytarabine, azacitidine, or ruxolitinib in 3 treatment groups. Dose escalation for 3 treatment groups will proceed independently. Approximately 3 to 6 subjects will be enrolled in each dose cohort. The total number of subjects will depend on the frequency of DLTs and the number of dose levels tested before the MTD or PAD is reached. The details of 3 combination groups are in Section 4.1.3.

9.2.4. Sample Size in Part 4

In Part 4, up to 4 expansion cohorts will be included to further evaluate the safety, tolerability, efficacy, PK, and PD of RP2Ds selected from Part 3. A Simon 2-stage design (Simon 1989) will be used for combination expansion cohorts C-TGA E1 and C-TGB E1 and the optional C-TGA E2. The response rates for the historical control (p_0), desired response rates for the combination (p_1), number of subjects needed in Stage 1 (n_1) and Stage 2 (n_2), total number of subjects in both stages (n), first stage threshold declaring cohort undesirable (r_1), the upper limit of the number of responses in n patients such that futility of the drug is concluded (r), and probability of early termination under p_0 ($PET[p_0]$) are provided for each expansion cohort (Table 23). The calculation is based on a 1-sided Type I error of 0.05 and power of 80%.

Table 23: Simon 2-Stage Design

Cohort	p_0	p_1	n_1	n_2	n	r_1	r	$PET(p_0)$
C-TGA E1	20%	40%	13	30	43	3	12	0.7473
C-TGB E1	20%	40%	13	30	43	3	12	0.7473
C-TGA E2 (optional)	20%	40%	13	30	43	3	12	0.7473

Up to 16 subjects will be enrolled in the C-TGC E1 cohort. [REDACTED]

9.3. Level of Significance

For the primary efficacy endpoints, the 1-sided Type I error will be controlled at 0.05 for each individual cohort expansion. For other endpoints, CIs will be reported at a 95% confidence level.

9.4. Statistical Analyses

9.4.1. Primary Analysis

- The clinical safety data (vital signs, ECGs, routine laboratory tests, and AEs) will be summarized using descriptive statistics (eg, mean, frequency) using the safety population.
- Part 4 only: Simon 2-stage design will be used to evaluate ORR, defined as the proportion of subjects who achieve CR or CRi, in C-TGA E1, C-TGB E1, and optional C-TGA E2. The interim analysis will be conducted once the first postbaseline bone marrow biopsies for Stage 1 subjects available. If fewer than or equal to a prespecified number of response is observed, the cohort will be discontinued. Otherwise, additional subjects will be enrolled for further evaluation.

9.4.2. Secondary Analyses

The secondary analysis includes the following:

- The clinical PK data (C_{max} , T_{max} , C_{min} , AUC_{0-t} , Cl/F) will be summarized using descriptive statistics (eg, mean, frequency) using the PK-evaluable population.
- Pharmacodynamic profile of INCB053914 defined by phosphorylation of Bcl-2-associated death promoter protein will be explored.

[REDACTED]

CONFIDENTIAL

CONFIDENTIAL

9.4.4. Safety Analyses

9.4.4.1. Adverse Events

Adverse events will be tabulated by the MedDRA preferred term and system organ class. Severity of AEs will be based on the CTCAE v4.03.

The subset of AEs considered by the investigator to have a relationship to study drug will be considered to be treatment-related AEs. If the investigator does not specify the relationship of the AE to study drug, the AE will be considered treatment-related. The incidence of AEs and treatment-related AEs will be tabulated.

9.4.4.2. Clinical Laboratory Tests

Laboratory test values outside the normal range will be assessed for severity based on the normal ranges for the clinical reference laboratory. The incidence of abnormal laboratory values and shift tables relative to baseline will be tabulated.

Laboratory data will be classified into CTC grades for AEs (CTCAE v4.03). The following summaries will be produced for the laboratory data:

- Tables showing number and percentage of subjects with worst postbaseline CTC grade (regardless of baseline value) will be produced. Each subject will be counted only for the worst grade observed postbaseline.
- Shift tables using CTC grades to compare baseline with the worst postbaseline value will be produced with CTC grade.
- For laboratory parameters where CTC grades are not defined, shift tables to the worst postbaseline value will be produced using the low/normal/high classifications based on laboratory reference ranges.

9.4.4.3. Vital Signs

Descriptive statistics and mean change from baseline will be determined for vital signs (blood pressure, heart rate, respiratory rate, and body temperature) at each assessment time. Vital sign results will be reviewed for clinically notable abnormalities (see [Table 24](#)), and subjects exhibiting clinically notable vital sign abnormalities will be listed. A value will be considered an "alert" value if it is outside the established range and shows a > 25% change from baseline.

Table 24: Criteria for Clinically Notable Vital Sign Abnormalities

Parameter	High Threshold	Low Threshold
Systolic blood pressure	> 155 mmHg	< 85 mmHg
Diastolic blood pressure	> 100 mmHg	< 40 mmHg
Pulse	> 100 bpm	< 45 bpm
Temperature	> 38°C	< 35.5°C
Respiratory rate	> 24/min	< 8/min

CONFIDENTIAL

CONFIDENTIAL

9.4.4.4. Electrocardiograms

Descriptive statistics and mean change from baseline will be determined for each ECG parameter at each assessment time. Electrocardiogram results will be reviewed for clinically notable abnormalities according to predefined criteria (Table 25). Subjects exhibiting clinically notable ECG abnormalities will be listed. Adverse events will be reported for clinically notable abnormalities that are considered clinically significant in the judgment of the investigator.

Table 25: Criteria for Clinically Notable Electrocardiogram Abnormalities

Parameter	High Threshold	Low Threshold
QTcF	> 460 msec	< 295 msec
PR	> 220 msec	< 75 msec
QRS	> 120 msec	< 50 msec
QT	> 500 msec	< 300 msec
RR	> 1330 msec	< 600 msec

QTcF = Fridericia correction.

9.4.4.5. Adverse Events of Special Interest

Adverse events of special interest include treatment-emergent ALT and AST elevations and treatment-emergent AEs related to liver toxicities.

Number (%) of subjects reporting any treatment-emergent ALT and AST will be summarized by grade. Any AEs related to liver toxicity will be identified using standard MedDRA queries.

9.4.5. Pharmacokinetic Analysis

The following PK parameters, C_{max} , T_{max} , C_{min} , AUC_t , and Cl/F (see Appendix B) will be calculated from the blood plasma concentrations of INCB053914 using standard noncompartmental (model-independent) PK methods. Pharmacokinetic calculations will be performed, if appropriate, using commercial software such as WinNonlin (Pharsight Corporation, Mountain View, CA). Nominal times will be used in all cases, except when the difference between the actual time and nominal time is greater than 15 minutes for samples collected up to 4 hours after administration and greater than 30 minutes for samples collected more than 4 hours after administration; in these cases, actual time will be used for PK analysis. Additional details of analyses will be described in the data analysis plan.

If there is a sufficient amount of plasma concentration data from this study, the data will be analyzed by standard population PK methods, using appropriate software (eg, NONMEM).

9.5. Interim Analysis

In Part 4, there are up to 3 planned interim analyses for futility in C-TGA E1, C-TGB E1, and an optional C-TGA E2. The Simon 2-stage design will be applied to each expansion cohort independently. During Stage 1, 13 subjects will be enrolled into each expansion cohort. If 3 or fewer of the first 13 evaluable subjects achieve an objective response, the cohort will be terminated for futility. In any cohort that exceeds this number of responders, additional subjects will be enrolled for Stage 2 evaluation.

CONFIDENTIAL

CONFIDENTIAL

Based on this early termination rule, the probability of early termination is 0.7473 under the assumption of historical control response rate; the probability of early termination is 0.1686 under the assumption of desired response rate.

The interim analysis for each expansion cohort will be conducted once the first postbaseline bone marrow biopsies for Stage 1 subjects within the cohort are available. Enrollment will be held at that time unless a sufficient number of responders (> 3 responders) have been observed before that time.

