5.1.4. Cytarabine

In the Part 3 C-TGA dose-finding cohorts and Part 4 combination expansion 1 (C-TGA E1) cohort, I-DAC will be administered to relapsed/refractory AML subjects as an open-label commercial product at a dose of 1 g/m² per day, 2-hour infusion on Days 1 through 5. A second induction cycle may be started between 15 days and 8 weeks after initiation of Cycle 1, at the discretion of the investigator, in subjects with residual leukemia upon bone marrow assessment during initial induction, provided all drug-related toxic effects had resolved to ≤ Grade 1. Up to 2 additional cycles may be given as consolidation therapy in subjects who achieved CR or

CONFIDENTIAL

CONFIDENTIAL

complete remission with incomplete platelet recovery, at the discretion of the investigator. The start of subsequent induction or consolidation cycles of I-DAC should be coordinated with the Day 1 of the INCB053914 21-day visit cycle when feasible.

If the Part 3 C-TGB dose-finding does not yield a tolerable combination of INCB053914 and azacitidine, or if the Part 4 C-TGB E1 Simon Stage 1 does not yield favorable efficacy data, then the sponsor may elect to evaluate INCB053914 in combination with a L-DAC regimen to treat elderly subjects (≥ 65 years) with newly diagnosed AML (*de novo* or secondary) who are unfit for intensive chemotherapy. In this event, L-DAC will be administered as an open-label commercial product at a dose of 20 mg SC on Days 1 through 10 of a 28- to 42-day cycle, depending upon hematologic recovery. Low-dose cytarabine therapy may continue until Protocol withdrawal criteria are met, or until subject's condition worsens, per investigator's clinical judgment, and warrants withdrawal.

Cytarabine dose modifications for toxicity may be made at the investigator's discretion.

Investigative sites must provide subjects with administration and storage instructions, as per cytarabine package insert or institution standard, for L-DAC SC syringes dispensed to subjects for administration away from the investigative site.

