Vital signs/height/weight ^f	7.5.3	X ^f	X ^f	X ^e	X	X ^f	X	X ^f	X ^f		
12-lead ECG	7.5.4	X	X			X		X	X		
AE assessment ^h	7.5.1	X	X	X	X	X	X	X	X		
Laboratory assessments	Table 10	X	X	X ^g	X	X	X	X	X		
Buccal swab	7.9.2	X									
AML disease assessments ⁱ	7.6	X	X		X		X	X		X	
Bone marrow examination ^j	7.9.1	X				X ⁱ					
Immunophenotyping ^k	7.6.5	X				When confirming CR					
Provide reminder card	7.10.2	X	X	X	X	X	X	X			
Poststudy disease status	6.4.2									X	

CR = complete remission.

^a During the treatment phase, subjects should be evaluated at the clinic in 21-day cycles in conjunction with the continuous administration of INCB053914. Subjects who receive subsequent reinduction or consolidation cycles of I-DAC should correlate the cycle start with Day 1 of a 21-day cycle visit whenever possible, following the Cycle 1 visit schedule (except inclusion/exclusion criteria review, any PK samples, and AML disease assessment [unless clinically indicated]). For example, a subject who starts a reinduction or consolidation regimen at Cycle 5 should have Cycle 5 Day 1, Day 5, and Day 15 study visits.

^b I-DAC will be administered as a 1 g/m² 2-hour infusion on Days 1 through 5.

CONFIDENTIAL

CONFIDENTIAL

- ^c Reinduction with I-DAC is permitted at the discretion of the investigator in subjects who have residual disease per Day 15 bone marrow examination provided all drug-related toxicities have returned to \leq Grade 1. Additionally, subjects who achieve CR or CRp may receive up to 2 cycles of I-DAC consolidation therapy at the discretion of the investigator.
- ^d All study drug for Cycle 1 will be dispensed at Cycle 1 Day 1; subject will bring unused study drug to clinic for compliance check on Cycle 1 Days 5, and 14. Drug will only be dispensed at Day 1 of all subsequent cycles and will bring unused study drug to clinic for compliance check on Day 11.
- ^e EOT visit - compliance check only.
- ^f Height only assessed at screening. Weight is only required at screening, Day 1 of each cycle, EOT, and the follow-up visit
- ^g During I-DAC infusions, vital signs and laboratory assessments may be performed per institution standard, however only preinfusion assessments on Day 1 and Day 5 are required to be entered into the eCRF.
- ^h Subjects must be followed for AEs for 30 days (+ 5 days) after the EOT visit (or after the last dose of study drug if the EOT visit was not performed.)

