- ⁱ Bone marrow biopsy and/or aspirates performed as clinically indicated or at Cycle 1 Day 15 (+ 2 weeks, depending upon chemotherapy recovery), Day 15 (+ 2 weeks) of any cycle where I-DAC is administered, and every other month as clinically indicated, or upon circulating blood cell recovery to assess antileukemic activity (cytogenetic testing is not required if CR is not presented). Note: For subjects who have a significant blast count reduction (as determined by the investigator) but have not completely cleared circulating blasts, the bone marrow during Cycle 2 is still strongly encouraged to be performed to assess the impact of treatment on the bone marrow blast content. See Section 7.6 for additional details.
- ^j If a biopsy is not possible or contraindicated, or if the tissue requirement cannot be satisfied, then this requirement may be waived with approval from the medical monitor. Subjects with a history of allogenic hematopoietic stem cell transplantation should have tissue collected and analyzed locally for the purposes of determining disease status (where applicable); however, their sample does not need to be processed for sequencing due to chimeric potential.
- ^k Immunophenotyping appropriate to AML will be conducted by flow cytometry at screening and when confirming CR.

CONFIDENTIAL

CONFIDENTIAL

Table 10: Laboratory Assessments for I-DAC Combination Cohorts

Visit Day Evaluation/Window	Section	Screening	Cycle 1			Subsequent Cycles ^a		EOT	Safety Follow-Up
		Day -28 to Day -1	D1	D5 ± 1 Day	D15 ± 1 Day	D1	D11 ± 4 Days	+ 3 Days	EOT + 30-35 Days
Overnight fast before assessments	Table 11			X	X				
Comprehensive blood chemistries	Table 21	X ^b	X ^b	X	X	X	X	X	X
Hematology with differential	Table 21	X ^b	X ^b	X	X	X	X	X	X
LFT panel ^c	Table 21	X ^b	X ^b	X	X	X	X	X	X
Coagulation panel ^c	Table 21	X ^b	X ^b		X	X		X	X
Urinalysis	Table 21	X				X ^d		X	X
Lipid panel	Table 21	X				X ^d			
Hepatitis screening	Table 21	X							
Serum pregnancy test	7.5.5.2	X	X ^e						X
PK – plasma ^f	7.8.1			X	X				

^a The Cycle 1 laboratory assessment schedule, with the exception of the overnight fast and PK sample collection, should be followed whenever I-DAC is administered during a cycle for reinduction or consolidation. Urinalysis and lipid panels should also be collected on Day 1 of cycles where I-DAC reinduction or consolidation treatment aligns with a cycle where these are scheduled (eg, Cycle 4).

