6.2.2. Visit Scheduling

Dates for subsequent study visits will be determined based on Day 1 (Cycle 1 Day 1) and should occur within the allotted visit window unless delayed for safety reasons. If study drug or SOC regimen administration must be interrupted at the beginning of a new planned cycle, the cycle will be delayed until the study drug or SOC regimen can be restarted as noted below. All planned assessments are shown in [Table 6](#), [Table 9](#), [Table 12](#), [Table 15](#), and [Table 18](#).

- Visit schedules for Part 3 and Part 4 C-TGA subjects receiving I-DAC will be based on 21-day cycles anchored to the INCB053914 administration. If I-DAC is given as reinduction or consolidation, the regimen start should align with a Day 1 of the 21-day cycle whenever possible.
- Visit schedules for Part 3 and Part 4 C-TGB subjects will be based on the start of subsequent cycles of azacitidine. Should a cycle start be delayed, subjects should continue to receive INCB053914 if appropriate.
- Part 3 and Part 4 C-TGC subjects will be seen every 4 weeks through Week 24 and every 12 weeks thereafter irrespective of whether INCB053914 and/or ruxolitinib are on hold. The study visits (Week 1, Week 2, etc) were named to align with the completion of a week's worth of study drug (ie, Week 1 is planned to occur on Study Day 8, or the end of 1 week of study drug).
- If the optional C-TGA E2 (L-DAC combination) is conducted, visit schedules for these subjects will be based on the start of subsequent cycles of L-DAC. Should a cycle start be delayed, subjects should continue to receive INCB053914 if appropriate.

During the treatment phase, regular study visits (physician visits) and laboratory-only visits will occur as denoted on the respective Schedules of Assessment and Laboratory Assessment tables.

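### C-TGA E1 futility look: the stated 0.1686 early-stop probability and 80% power hold only if no Stage 1 response is still pending when the cohort is stopped, and the plan has no rule for pending subjects

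*Protocol*

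**What the plan says.** **Design.** Protocol Table 23 and SAP Table 1 give the Simon two-stage design for C-TGA E1: p0 = 20%, p1 = 40%, n1 = 13, r1 = 3, n = 43, r = 12, with 1-sided alpha 0.05 and power 80%. Protocol 9.5 adds that "the probability of early termination is 0.1686 under the assumption of desired response rate".

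**Timing and action.** Under Protocol 9.5 the interim "will be conducted once the first postbaseline bone marrow biopsies for Stage 1 subjects within the cohort are available"; SAP 11 says the same. Protocol 9.5 then holds enrollment unless more than 3 responders have already been seen. Protocol 9.4.1 states the consequence: "If fewer than or equal to a prespecified number of response is observed, the cohort will be discontinued".

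**The marrow schedule.** Table 9 footnote i places the first marrow at Cycle 1 Day 15 (+ 2 weeks). Footnote c permits I-DAC reinduction in "subjects who have residual disease per Day 15 bone marrow examination". Protocol 5.1.4 sets the window: "A second induction cycle may be started between 15 days and 8 weeks after initiation of Cycle 1". Footnote i also lists a marrow at "Day 15 (+ 2 weeks) of any cycle where I-DAC is administered" and one "upon circulating blood cell recovery to assess antileukemic activity".

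**The endpoint.** Protocol 2.2.1 defines ORR as CR or CRi and gives no time limit. SAP 7.4.1.2.1 takes the best response up to the first treatment failure, relapse or progression. It also counts morphologic leukemia-free state (MLFS), PR and peripheral blood blast response as responses.

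**The concern.** Simon's early-termination probability and power treat the Stage 1 count as final. Here the look is triggered by a marrow that the plan also uses to decide who may receive more induction. A response can be pending at that moment by two routes:

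- **Reinduction.** A subject with residual disease at Day 15 may remit after a second induction. This route is open unless residual leukemia on the first marrow is itself recorded as treatment failure, which would end the best-response window.
- **Count recovery.** Under CR/CRi, a clear marrow without sufficient count recovery is not yet a response. This route is narrower than it looks, because CRi in Appendix D accepts residual neutropenia or thrombocytopenia and the first marrow may move by 2 weeks for recovery. It closes if the SAP responder set applies, since MLFS then counts at once.

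At stake is the termination of an active cohort on an incomplete count. That cannot be reversed once enrollment has ended, and the stated wrongful-stop risk would then not describe the rule in use.

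**Working it through.** **1. Reproduce the stated design.** Inputs are n1 = 13, r1 = 3, n2 = 30, r = 12 from Protocol Table 23.

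- PET(p) = P(Bin(13, p) ≤ 3). At p = 0.4: 0.0013 + 0.0113 + 0.0453 + 0.1107 = 0.1686. At p = 0.2: 0.7473. Both match.
- P(reject) = sum over x1 ≥ 4 of P(X1 = x1) × P(Bin(30, p) ≥ 13 − x1). At p = 0.4: 0.8002. At p = 0.2: 0.0496.

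The design arithmetic is correct, and power has almost no slack above 80%.

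**2. Allow responses to be pending.** Two quantities are needed, and the documents give neither, so both are assumptions:

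- k = how many of the 13 have only their first marrow at the decision;
- f = share of eventual responders visible at that marrow.

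The other 13 − k subjects are fully visible, Bin(13 − k, p). Each of the k subjects is a visible responder with probability fp, a late responder with probability (1 − f)p, or a non-responder with probability 1 − p. The cohort stops if visible responders ≤ 3. Otherwise it succeeds if all Stage 1 responders, late ones included, plus Bin(30, p) total at least 13.

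| Scenario | PET at 40% | Power at 40% | Type I error at 20% |
|---|---|---|---|
| As stated (none pending) | 0.1686 | 0.8002 | 0.0496 |
| k = 2, f = 0.95 | 0.1743 | 0.7950 | 0.0490 |
| k = 4, f = 0.90 | 0.1921 | 0.7788 | 0.0471 |
| k = 4, f = 0.75 | 0.2307 | 0.7434 | 0.0433 |
| k = 13, f = 0.90 | 0.2536 | 0.7220 | 0.0413 |

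The last row can be checked directly: P(Bin(13, 0.9 × 0.4 = 0.36) ≤ 3) = 0.2536. Setting k = 13 is the extreme for k, because earlier enrollees would usually have longer follow-up.

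Loss of power: 80.0 − 79.5 = 0.5 points in the mildest row, and 80.0 − 72.2 = 7.8 points in the last.

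**3. When is anything pending?** Two open definitions decide it.

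| | CR/CRi counted (Protocol) | SAP responder set |
|---|---|---|
| Residual leukemia is not treatment failure | both routes open | reinduction route open |
| Residual leukemia is treatment failure | count-recovery route open | both closed; stated figures stand |

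Appendix D applies resistant disease to patients alive at least 7 days after initial treatment. Day 15 is 10 days after the Day 5 dose, so the treatment-failure reading is possible. Permitting reinduction in exactly these subjects points the other way.

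**4. How long would waiting take?** The first marrow is at Day 15 to 29. Protocol 6.2.2 says: "If I-DAC is given as reinduction or consolidation, the regimen start should align with a Day 1 of the 21-day cycle whenever possible". Aligned starts within 8 weeks are Day 22 or Day 43, so the following marrow is due by Day 50 or Day 71. The latest unaligned start is Day 57, with the marrow by Day 85. The added hold is therefore 71 − 29 = 42 days (6 weeks) or 85 − 29 = 56 days (8 weeks). It is longer if reinduction or assessment is delayed, which Protocol 5.2.4 and 7.6 allow.

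**The case against.** The best defense is that the rule has no time cut. Protocol 9.5 and SAP 11 terminate if 3 or fewer of the first 13 evaluable subjects *achieve* a response; the marrow sentence only says when the analysis is run, and enrollment is then *held*. If held means a pause until outcomes are known, 0.1686 and 80% are right. This reading stands as possible, and it means the documents do not establish that the cohort must be stopped at the first marrow. But Protocol 9.4.1 discontinues on what is observed, neither document defines a second look or a waiting period, and evaluable is not defined for Part 4.

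Three further points stand. The effect disappears under one combination of definitions, and one half of that combination is what the SAP says. Its size is pure assumption. And parts of Protocol 7.6 and of SAP 7.1 and 7.4.1 are redacted, so a follow-up rule there cannot be excluded, although the interim sections show no redaction.

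A reader might infer that the trial has materially lower power than stated, or that the false-positive rate is raised. The documents support neither: they give no time-to-response or accrual data, and late responses can only make the stop more frequent, which lowers type I error. Some sponsors would also accept an early look to limit exposure to an inactive regimen. That is a legitimate trade, provided the stated figures describe it.

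**Conclusion.** The point holds as a conditional one. For C-TGA E1 the published PET(40%) of 0.1686 and power of 80% are correct only if the Stage 1 count at the decision equals the final Stage 1 count, and the text does not secure that. The illustrative cost is about 0.5 points of power (2 of 13 subjects with only a first marrow, 95% of responders visible) to about 8 points (all 13, 90% visible). These are examples, not bounds or estimates. There is no loss if residual leukemia is treatment failure and the SAP responder set applies, or if the hold is a true wait. The change is still worth making: the wording admits a wrongful stop, power has no slack, and the remedy is cheap. Separately, the SAP responder set contradicts the CR/CRi endpoint that the 3/13 and 12/43 thresholds are meant to test.

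**What to change.** 1. Use the Protocol's CR/CRi definition for both the Stage 1 and the final count, and correct SAP 7.4.1.2.1 accordingly.
2. In Protocol 9.4.1 and 9.5 and SAP 11, state that enrollment is held at 13 once first marrows are in and that the cohort proceeds as soon as more than 3 responders are seen. State that it is terminated only when each of the 13 has responded, had an event that ends best response, completed the response assessments already scheduled (including marrow and counts after any reinduction), or reached a calendar cut-off the sponsor fixes in advance. Subjects off treatment without progression stay in disease-status follow-up until that cut-off. The same sentence can serve C-TGB E1 and the optional C-TGA E2, which are less clearly affected.
3. State whether residual leukemia leading to permitted reinduction ends best response.
4. Whichever trigger is chosen, state that PET and power are conditional on Stage 1 responses being complete by the cut-off. Even the rule in item 2 can leave a late response uncounted, so it does not restore the figures exactly.

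Cost: wording in two documents, with no extra subjects and no new marrow procedure. The downside is a longer enrollment hold, about 6 to 8 weeks and more if reinduction is delayed, and only in a cohort with 3 or fewer responders.
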